9.4.2 Treatment Administration

At Visit 2, eligible patients will receive [REDACTED] tubes of RHOFADE™ Topical Cream, 1%. Study product will be applied in the clinic at Visits 2, 3, and 4. Patients will be instructed to apply the study product at home once daily, at approximately the same time of day, on non-visit days,

CONFIDENTIAL PROTOCOL

An Evaluation of the Reduction in Erythema by RHOFADETM (oxymetazoline hydrochloride) Topical Cream, 1% (Allergan) in Adult Patients with Moderate to Severe Persistent Facial Erythema Associated with Rosacea.

for a total of 15 ± 2 days. The last dose should be applied during Visit 4. Patients should not to dose within approximately 24 hours before any study visit.

[REDACTED]

The cleanser should not be shared with others (i.e., the cleanser should only be used by the patient who receives it from the investigative site). Patients will also be instructed not to apply the study product to cuts, abrasions, eczematous skin and sunburned skin and not to use "waxing" as a depilatory method on skin treated with the study product.

Each patient will be provided with a dosing diary in which they will be required to record dosing dates and times. These diaries should be brought to Visits 2, 3, and 4 so that the study staff may check compliance and file it in the patient's source documentation. At the end of the study, they will be retained in the patient's file as source documentation.

9.4.3 Study Blind

This is an open-label study.

9.4.4 Study Product Shipment, Storage, and Retention

The study products will be shipped in bulk to the Investigator's site from a centralized location. The Principal Investigator is responsible for ensuring that all study products are stored in a locked, secure location, with access limited to the Investigator and his/her designee(s). An accurate inventory of the study product will be maintained in accordance with federal regulations.

The label will include the following information:

- Protocol number
- Randomization number
- Space for patient's initials
- Statement that the study product is for Investigational Use only
- Space for dispensing date and the Sponsor's name

In addition all patients will be provided with written instructions on how to use the study product.

Each patient will receive [REDACTED] tubes of study product. This quantity will suffice for the entire study duration.

Storage Conditions

While at the research site, the study product is to be stored in a secure, locked location, at controlled room temperature of 20-25°C (68-77°F) with excursions permitted to 15-30°C (59-86°F). Any excursions from the above temperature range will require prompt notification to [REDACTED]; thereafter [REDACTED] will notify the Sponsor.

CONFIDENTIAL PROTOCOL

An Evaluation of the Reduction in Erythema by RHOFADETTM (oxymetazoline hydrochloride) Topical Cream, 1% (Allergan) in Adult Patients with Moderate to Severe Persistent Facial Erythema Associated with Rosacea.

Retention

As this is not a bioanalytical or bioequivalence study, no retention samples are needed.

9.4.5 Method of Assigning Patients to Treatment Groups

Patients will be assigned to treatment in an open-label fashion. At Visit 2, eligible patients will be assigned a randomization number in ascending sequential order, starting with the lowest number available.

9.4.6 Compliance

Patients will be provided with a diary to record the time and date of dosing, other concomitant medications, and AEs.

[REDACTED] . Compliance with dosing will be verified by the use of the patient diaries. Compliance criteria are as outlined in the table below:

For patients who have completed the study:

Study Design		
Visit 4	Treatment Duration	Required Doses
Day 13-17	13-17 Days	15

For patients who are early terminated, compliance will be based off their duration in the study, up to the time they are considered early terminated. For example, if a patient is dropped after 10 days of participation and doses 8 times, their percent compliance is 80%.

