4.0 SYNOPSIS

Protocol Number	PRG-NY-17-013
Title	An Evaluation of the Reduction in Erythema by RHOFADE™ (oxymetazoline hydrochloride) Topical Cream, 1% (Allergan) in Adult Patients with Moderate to Severe Persistent Facial Erythema Associated with Rosacea.
Objectives	
The objectives of this study are to:
 
1. Evaluate the reduction of erythema by the marketed formulation RHOFADE™ (oxymetazoline hydrochloride) Topical Cream, 1% in the treatment of moderate to severe persistent (non-transient) facial erythema associated with rosacea
Sponsor	Perrigo New York, Inc.
Study Product	RHOFADE™ (oxymetazoline hydrochloride) Topical Cream, 1% (Allergan)
Route of Administration	Topical
Dosage Regimen	
Patients will be instructed to apply [REDACTED] once daily at approximately the same time of day for 15 ± 2 days. Patients will apply the first dose of study product at Visit 2 under supervision of the study staff. The last dose should be administered at

CONFIDENTIAL PROTOCOL

An Evaluation of the Reduction in Erythema by RHOFADETM (oxymetazoline hydrochloride) Topical Cream, 1% (Allergan) in Adult Patients with Moderate to Severe Persistent Facial Erythema Associated with Rosacea.

	
the clinic during Visit 4. Each patient is expected to receive up to 17 doses of study product.

Study Design	An open-label, single-product, single-site, multiple-dose study
Study Population	Approximately 50 males and non-pregnant females, 18 years of age and older, with a clinical diagnosis of persistent (non-transient) facial erythema associated with rosacea
Confinement	Patients will remain confined to the clinic [REDACTED] at Visits 2, 3, and 4.

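### Protocol 9.4.6 sets a fixed 15 doses for completers whose once-daily schedule gives 13 to 17, so their compliance figure depends on the day of Visit 4 as well as on adherence

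*Protocol*

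**What the plan says.** Protocol 9.4.6 verifies dosing from the patient diaries and continues: "Compliance criteria are as outlined in the table below". The table has one row, for completers. It pairs a Visit 4 on Day 13 to 17 and a treatment duration of 13 to 17 days with a single entry of 15 under the column "Required Doses". No readable text says how a completer's percentage is calculated, and a sentence just before the table is redacted.

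For early terminators the same section uses another basis: "compliance will be based off their duration in the study, up to the time they are considered early terminated". Its example is that "if a patient is dropped after 10 days of participation and doses 8 times, their percent compliance is 80"%.

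The schedule is given elsewhere. In the Synopsis (Dosage Regimen), "Patients will apply the first dose of study product at Visit 2 under supervision of the study staff", and "Each patient is expected to receive up to 17 doses of study product". Protocol 9.4.2 has one application daily, with clinic doses at Visits 2, 3 and 4, and adds: "The last dose should be applied during Visit 4". The next sentence of 9.4.2 reads "Patients should not to dose within approximately 24 hours before any study visit".

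The Per-Protocol definition (Protocol 10.4.1, SAP 7) includes a criterion on proper application of the product. The detail of that criterion is blacked out in both documents.

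**The concern.** A range of five durations is matched to one dose count. A completer seen on Day 13 has 13 dosing days and one seen on Day 17 has 17, yet both are held to 15. The next paragraph of 9.4.6 adjusts the expected count to the patient's own time in the study. Two rules in one section therefore define compliance differently, and the completer rule mixes adherence with visit scheduling.

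Two things are at stake. Completers' compliance figures would not be comparable with one another. Also, if the redacted part of the Per-Protocol dosing criterion uses the 9.4.6 figure, a patient's place in that population could depend partly on which permitted day the final visit fell.

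**Working it through.** **Inputs.** First dose at Visit 2, Day 1 (Synopsis; Protocol 9.1). One dose per day, with the last at Visit 4 (9.4.2). Visit 4 on Day d = 13 to 17 (9.4.6, 10.4.1). Fixed count of 15 (9.4.6).

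**The plan's own figures.** The early-terminator example reproduces: 8/10 = 80%. The 17-dose maximum also reproduces: one dose per day from Day 1 to Day 17 is 17 − 1 + 1 = 17. Neither figure is miscalculated; the problem is one of definition.

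**What the example implies.** A patient dropped after 10 days has passed Visit 3 (Day 7 ± 2). If one pre-visit dose were deducted, the result would be 8/9 = 88.9%. The stated 80% needs a denominator of 10, so 9.4.6 itself counts one dose per day.

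**Completers.** Scheduled doses are s = d. There are two ways to use the 15:

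| Visit 4 day | Scheduled doses s | Full adherence, s/15 | Full adherence, s/s | Doses above or below 15, s − 15 |
|---|---|---|---|---|
| 13 | 13 | 86.7% | 100% | −2 |
| 14 | 14 | 93.3% | 100% | −1 |
| 15 | 15 | 100.0% | 100% | 0 |
| 16 | 16 | 106.7% | 100% | +1 |
| 17 | 17 | 113.3% | 100% | +2 |

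*As a denominator* (doses taken over 15): each visit day moves the score by 1/15 = 6.7 points, the same as one dose. Across the window the shift is 4/15 = 26.7 points. One missed dose gives 12/15 = 80.0% on Day 13 and 16/15 = 106.7% on Day 17. Against scheduled doses these are 12/13 = 92.3% and 16/17 = 94.1%.

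*As a required count*: a fully adherent Day 13 or Day 14 completer cannot reach 15. A Day 16 or Day 17 completer reaches it with one or two doses missed.

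**Illustration with assumed limits.** The readable text gives no limit; suppose a lower limit of 75% or 80%.

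- A Day 13 completer with two isolated misses took 11/13 = 84.6% of scheduled doses but scores 11/15 = 73.3%, below either limit.
- A Day 17 completer with five isolated misses took 12/17 = 70.6% but scores 12/15 = 80.0%. That is above 75%, and it meets 80% only if the limit is inclusive. Other Per-Protocol criteria could still exclude this patient.

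**Sensitivity to the 24-hour statement.** Suppose it removes the doses on the days before Visits 3 and 4. Then s = d − 2 = 11 to 15, full adherence scores 73.3%, 80.0%, 86.7%, 93.3% and 100%, and only a Day 17 completer can reach 15. The spread by visit day is still 26.7 points.

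**The case against.** **The governing rule may be hidden.** The redacted sentence in 9.4.6, or the redacted Per-Protocol text, may hold the completer formula, the limits or a tolerance around 15. This stands. No misclassified patient can be shown from the readable text, and the percentages above are conditional on scoring over 15.

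**Fifteen may be a deliberate nominal figure.** It is the centre of the 15 ± 2 day window. Under the percentage reading, a fully adherent patient fails only if the limits are tighter than 86.7% to 113.3%. This also stands. It does not explain why the next paragraph uses actual duration: a patient who leaves after 12 days and 12 doses scores 12/12 = 100%, while a Day 13 completer with 13 doses would score 86.7%.

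**The required-count reading is weak.** A reader might infer that 15 is a hard minimum that early completers fail. Only the column heading supports this. The one score shown in 9.4.6 is a percentage, and a hard minimum would make part of the table's own window impossible to satisfy.

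**The consequences are limited.** A reader might also infer that adherent patients are wrongly dropped from the Per-Protocol population, or that efficacy results are biased. The documents support neither:

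- The limits cannot be read.
- Early terminators are already outside the Per-Protocol population on the readable criteria, which require the final visit on Day 13 to 17, so the mismatch with their rule has no readable effect there.
- The mITT and Safety populations have no compliance criterion.
- No readable SAP analysis uses the compliance percentage.
- With one product there is no between-arm comparison to distort.

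**Conclusion.** The inconsistency is real and can be seen without the redacted text: one dose count for 13 to 17 scheduled doses, beside a per-day rule in the same section. If completers are scored over 15, equally adherent patients differ by up to 26.7 points, from 86.7% to 113.3%, through visit day alone. If 15 is instead a required count, full adherence on Day 13 or 14 falls short of it. Either way the figure reflects visit timing as well as adherence.

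The range assumes a dose on every calendar day from Visit 2 through Visit 4; the spread, though not the level, is the same under the stricter reading of the 24-hour statement. That the redacted Per-Protocol text contains compliance limits is inferred from its position. Any effect on Per-Protocol membership is undetermined. Importance is minor, but the plan should be corrected.

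**What to change.** - **Protocol 9.4.6:** reconcile the table with the once-daily schedule by computing each completer's percent compliance as doses taken over doses scheduled from Visit 2 through the actual Visit 4 day. This is the per-day basis the section already uses for early terminators, whose rule can stay as written.
- **SAP:** use the same derivation, if it is not already in the redacted text.
- **Per-Protocol limits:** before database lock, the sponsor should confirm that they suit the new denominator. They may have been set around 15 and should not be carried over unchecked.
- **Protocol 9.4.2:** the once-daily and 24-hour pre-visit statements must be reconciled so that the scheduled count is unambiguous. No dosing rule is proposed here.

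The cost is a wording change, a small change to the compliance derivation and a check of the limits. Diaries already record the date and time of each dose, so no new data are needed.

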9.5 Study Conduct

9.5.1 Visit 1 – Screening/Baseline (Day -28 to -1)

CONFIDENTIAL PROTOCOL

An Evaluation of the Reduction in Erythema by RHOFADE™ (oxymetazoline hydrochloride) Topical Cream, 1% (Allergan) in Adult Patients with Moderate to Severe Persistent Facial Erythema Associated with Rosacea.

A series of seven horizontal black bars of varying lengths, decreasing from left to right. The bars are positioned at different vertical intervals, creating a stepped effect. The first bar is the longest and is located at the top. The second bar is shorter and is located below the first. The third bar is the shortest and is located below the second. The fourth bar is longer than the third and is located below the third. The fifth bar is longer than the fourth and is located below the fourth. The sixth bar is longer than the fifth and is located below the fifth. The seventh bar is the longest and is located at the bottom.

9.5.2 Visit 2 – Baseline (Day 1)

This figure displays a 10x10 grid of black and white bars, representing a 2D convolutional feature map. The bars are arranged in a grid pattern, with varying widths and heights. The bars are black on a white background, and the grid lines are white on a black background. The bars are of different sizes and are distributed across the grid, with some being taller and wider than others. The overall pattern is a mix of black and white bars, creating a visual representation of a convolutional feature map.

CONFIDENTIAL PROTOCOL

An Evaluation of the Reduction in Erythema by RHOFADE™ (oxymetazoline hydrochloride) Topical Cream, 1% (Allergan) in Adult Patients with Moderate to Severe Persistent Facial Erythema Associated with Rosacea.

9.5.3 Visit 3 – Interim Visit (Day 7 ± 2 Days)

The image consists of several thick, horizontal black bars of varying lengths. These bars are positioned in a staggered, non-overlapping manner. The lengths of the bars decrease from left to right. The background is a solid white color. The bars have a high contrast, pixelated appearance, suggesting they are digital artifacts or heavily processed images.

CONFIDENTIAL PROTOCOL

An Evaluation of the Reduction in Erythema by RHOFADE™ (oxymetazoline hydrochloride) Topical Cream, 1% (Allergan) in Adult Patients with Moderate to Severe Persistent Facial Erythema Associated with Rosacea.

9.5.4 Visit 4 – End of Study Visit or Early Termination (Day 15 ± 2 Days)

CONFIDENTIAL PROTOCOL

An Evaluation of the Reduction in Erythema by RHOFADETTM (oxymetazoline hydrochloride) Topical Cream, 1% (Allergan) in Adult Patients with Moderate to Severe Persistent Facial Erythema Associated with Rosacea.

[REDACTED]

[REDACTED]

[REDACTED]

[REDACTED]

[REDACTED]

[REDACTED]

[REDACTED]

[REDACTED]

[REDACTED]

9.6 Study Procedures

9.6.1 Informed Consent

At Visit 1, before performing any study-related procedures, the patient must sign the IRB-approved ICF. The ICF will be reviewed and approved by an IRB before study commencement. No patient will be entered into the study without reading, understanding, and signing an ICF. If any other language is required, translation will be performed by a certified translator.

9.6.2 Medical History

At Visit 1, patients will be questioned about personal medical history, including rosacea history.

9.6.3 Demographics

At Visit 1, each patient will be required to provide basic demographic information (i.e., date of birth, sex, ethnicity, and race).

9.6.4 Pregnancy Test

All females of childbearing potential will have a urine pregnancy test performed at Visits 1, 2, and 4. The test must be negative at Visits 1 and 2 for the patient to be eligible for inclusion in the study. If the patient is female and not considered of childbearing potential, then the reason must be documented in the patient's source documents.

Any patient who becomes pregnant during the study should be discontinued and end of study procedures (Visit 4) completed. The outcome of the pregnancy should be followed by the Investigator to the conclusion of the pregnancy. The pregnancy will be reported as an AE.

9.6.5 Vital Signs

The patient's vital signs will be recorded [REDACTED] at each visit.

9.6.6 Concomitant Medication Use

At Visit 1, patients will be questioned about medication use [REDACTED]. At all subsequent visits, patients will be questioned about ongoing or new concomitant medication use.

CONFIDENTIAL PROTOCOL

An Evaluation of the Reduction in Erythema by RHOFADETTM (oxymetazoline hydrochloride) Topical Cream, 1% (Allergan) in Adult Patients with Moderate to Severe Persistent Facial Erythema Associated with Rosacea.

At Visit 2, any patient who has used medications restricted by the protocol may be discontinued from the study. If discontinued, all early termination procedures (Visit 4 procedures) should be performed.

9.6.7 Adverse Events

At the end of Visit 1, patients will be questioned about any AEs that occurred during the visit. At Visits 2, 3 and 4, patients will be questioned regarding any changes in their medical status since their previous visit. Any significant health changes observed after enrollment into the study will be reported as AEs, as deemed appropriate by the Investigator.

9.6.8 Lesion Count

At Visits 1, 2, and 4, the number of inflammatory lesions (i.e., papules and pustules) on the facial area, including the nose, will be counted and recorded. Wherever possible the same individual should attempt to perform lesion counts at all visits for an individual patient.

9.6.9 [REDACTED]

9.6.10 [REDACTED]

9.6.11 [REDACTED]

9.6.12 Inclusion/Exclusion Criteria Review

At Visits 1 and 2, inclusion/exclusion criteria will be reviewed to ensure patients' eligibility for participation in the study.

CONFIDENTIAL PROTOCOL

An Evaluation of the Reduction in Erythema by RHOFADE™ (oxymetazoline hydrochloride) Topical Cream, 1% (Allergan) in Adult Patients with Moderate to Severe Persistent Facial Erythema Associated with Rosacea.

9.6.13

A vertical column of ten black rectangular bars, each preceded by a short black dash. The dashes are positioned to the left of the first bar in each row.

9.6.14 Dispense Study Product

The site will dispense one tube of study product at Visit 2 along with dosing instructions. The site will ensure the study product logs are reported correctly.

9.6.15 Dosing

Patients will dose at the site during Visits 2, 3, and 4. After pre-dose assessments are complete, patients will wash and dry their face with the supplied cleanser and apply the study product according to the dosing instructions.

9.6.16 Dispense Patient Diary/Supplies

Patients will be provided with a dosing diary at Visits 1, 2, and 3 along with instructions on how to complete the diary. Patients will be asked to record AEs and concomitant medications throughout the study. Starting at Visit 2, patients will also be asked to record the time and date of each dose.

At Visit 1, the patient will be provided with the mild non-medicated cleanser (e.g., Dove® Sensitive Skin or similar) and sunscreen (e.g., Neutrogena SPF 45 or similar). The use of the sunscreen should be documented on the concomitant medication page on the source documents

CONFIDENTIAL PROTOCOL

An Evaluation of the Reduction in Erythema by RHOFADE™ (oxymetazoline hydrochloride) Topical Cream, 1% (Allergan) in Adult Patients with Moderate to Severe Persistent Facial Erythema Associated with Rosacea.

and eCRFs. Additional cleanser and sunscreen may be provided during the study at the request/need of the patient.

9.6.17 Collect/Review Patient Diary

At Visits 2, 3, and 4, patient diaries will be collected and reviewed for compliance with the protocol.

9.6.18 Collecting Study Product

The study product will be collected by the site at Visit 4. The site will ensure the study product logs are reported correctly.

9.7 Adverse Reactions

In studies with RHOFADE™ (oxymetazoline hydrochloride) Topical Gel treated for 29 days, adverse reactions related to treatment reported by at least 1% of subjects treated included erythema, flushing, skin burning sensation, contact dermatitis, dermatitis, warm skin, paresthesia, acne, skin pain, blurred vision, and nasal congestions.

9.7.1 Deviation from the Protocol for Individual Patients

When an emergency occurs requiring a patient's departure from the protocol, this shall apply only for that patient. In such circumstances, the Investigator or other physician in attendance shall notify the Medical Monitor or Perrigo by telephone and follow up with a written description within one day. The overseeing IRB should also be notified.

9.7.2 Adverse Event Definitions

An AE is defined as any untoward medical occurrence in a patient administered a medicinal product and which does not necessarily have to have a causal relationship with this treatment. An AE can therefore be any unfavorable and unintended sign (for example, an abnormal laboratory finding), symptom, or disease temporally of the use of a medicinal product, whether or not considered related to this medicinal product.

A serious adverse event (SAE) is an AE that results in any of the following outcomes:

- Death
- Life-threatening event (i.e., the patient was, in the opinion of the Investigator, at immediate risk of death from the event as it occurred. It does not include an event that, had it occurred in a more severe form, might have caused death)
- Requires in-patient hospitalization or prolongs hospitalization
- A persistent or significant disability/incapacity or substantial disruption of the ability to conduct normal life functions
- Congenital anomaly/birth defect
- Other AEs that may be considered serious based upon appropriate medical judgment, may jeopardize the patient and may require medical or surgical intervention to prevent

CONFIDENTIAL PROTOCOL

An Evaluation of the Reduction in Erythema by RHOFADETM (oxymetazoline hydrochloride) Topical Cream, 1% (Allergan) in Adult Patients with Moderate to Severe Persistent Facial Erythema Associated with Rosacea.

one of the outcomes listed above (e.g., allergic bronchospasm requiring intensive treatment in an emergency room or home, blood dyscrasias or convulsions that do not result in hospitalization, or the development of drug dependency or drug abuse).

Immediately Reportable Adverse Events (IRAE): Any SAE or any AE that necessitates discontinuation of study product, including pregnancy.

Unexpected Adverse Event: Any adverse drug experience, the specificity or severity of which is not consistent with the current approved product labeling (package insert) for the study product, the Investigator's Brochure, or as described in the clinical protocol and consent materials.

